1.2. Study design

The trial is designed as a prospective, multi-center, randomized, controlled and parallel arm comparison.

Once informed consent form (ICF) signed, the patients will perform a screening visit (V1) to confirm trial eligibility. The eligible patients will be randomized by Interactive Web Response System (IWRS) to determine the Investigational Medicinal Product (IMP) to be injected. They will undergo a DSC-MRI perfusion using Elucirem® or Dotarem® (MRI visit - V2).

A safety visit (V3) will be performed 1 day after the MRI visit by phone. Confirmation of tumor grade diagnosis, if available, will be collected up to 30 days after visit 2.

The randomization scheme will allocate patients in a 1:1 ratio to the two parallel arms. Stratification by glioma grades (low grades versus high grades) between the two arms will be managed by IWRS based on the diagnosis collected at screening.

Images will be evaluated by both on-site and off-site readers.

For on-site reads, at least one experienced neuroradiologist will be appointed in each investigational site at the start of the trial to read perfusion images of patients included at the site.

For off-site reads, all images will be sent to an Imaging Core Laboratory (ICL) which will prepare the images for evaluation. The off-site images evaluation will be performed by two Independent Blinded Readers (IBR) experienced in perfusion MRI and brain tumors. In case of discordance (for number of lesions detected, localization of the lesion(s), diagnostic quality of the CBV map (primary criterion), rCBV quantification (only the glioma grade, not the rCBV value) and/or visual evaluation of the T2* signal intensity time curve, including the confidence in the diagnosis), a consensus meeting will be organised in order to reach an

agreement. Matching of the lesion(s) assessed by the IBR, with the histopathological data provided by the site, if any, will be performed by a third reader (see Imaging Charter V1.0).

[figure not shown]
For this study, only off-site readers will be blinded to the nature of the Investigational Medicinal Product (IMP) injected.

The diagnosis obtained from previous (qualifying) imaging examinations will be considered as medical history to assess inclusion criteria. All the trial analyses will be only based on the images obtained through the trial MRI.

During the trial, the safety of the patients will be monitored and assessed based on the reporting of AEs.

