2.2.2. Secondary efficacy Criteria

On-site Evaluation of CBV Map Diagnostic Quality

The same 4-point scale, described in [§2.2.1](#), is used to assess the diagnostic quality of CBV map generated by the **on-site readers**.

Quantification of the relative CBV for differentiating tumor grade (off-site assessment)

For each DSC-MRI perfusion, the rCBV will be calculated on the CBV perfusion map. The regions of interest (ROIs) will be placed by off-site readers on the tumors (i.e. lesions) for providing tumor CBV and on normal tissue (contralateral normal-appearing white matter) for providing referenced CBV.

Localization and size of the tumors assessed by the off-site readers will be compared to the targeted tumor concerned by the standard of truth for grading gliomas in order to check if there is a correspondence between SOT tumor and one of the tumors assessed by the off-site readers. Standard of truth will be the histopathological results collected on site (diagnosis based on the 2021 WHO classification of CNS tumors).

Assessment and evaluation of the T2* signal intensity time curve (on-site and off-site assessment)

T2* signal intensity time curve will be visually assessed by on-site and off-site readers for the reliability of the curve in providing sufficient information for diagnosis purpose. If the curve is assessed as reliable, the full-width at half-maximum (FWHM) and the maximum signal drop will be measured by off-site readers only.

Readers will record their confidence in diagnosis based on the reliability of the curve using a 5-point scale:

- 1 = nil: very uncertain
- 2 = poor: uncertain
- 3 = moderate: moderately certain
- 4 = high: good certainty
- 5 = excellent: very certain

The rCBV, T2* signal intensity, FWHM and maximum signal drop will be assessed at lesion level. Analyses relative to rCBV will be performed at patient or patient / reader level and analyses relative to T2* signal intensity, FWHM and maximum signal drop will be performed at lesion or lesion / reader level. Of note, analyses for on-site reader at patient level are equivalent to lesion level as only one lesion is considered.

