3. STATISTICAL METHODS

3.1. General considerations

After the database lock, the statistical analysis will be performed by a CRO Biostatistician on the basis of the present document.

A quality control of the statistical analysis will be performed to ensure the reliability of the results.

Thorough description of all parameters reported will be presented separately by arm. Summary tabulated results will be provided by arm and assessment time, if relevant, or they will be replaced by the corresponding individual data listings if too few subjects are concerned.

Tabulations of quantitative parameters will include the following summary statistics: Number of Patients / Mean / Standard Deviation (SD) / Minimum / Median / Maximum. The mean and median will be reported to 1 decimal more than the data; SD to 2 more decimals than the data; and minimum and maximum to the same number of decimals as the data.

Rules for rounding decimals (example= the weight):

If decimal is <0.5 then round the number down (example: 65.3kg is rounded to 65kg)

If decimal is ≥ 0.5 then round the number up (example: 65.6kg is rounded to 66kg)

Tabulations of frequencies for categorical data will include all possible categories and will display the number of observations in a category as well as the percentage (%) relative to the respective arm. Percentages will be rounded to one decimal place.

The baseline value will be defined as the last available value prior to administration of the investigational product.

All statistical tests will be performed at the significant threshold of 2.5% one sided (5% two-sided).

SAS® Version 9.4 (or later version) will be used for all descriptive summaries and inferential analyses.

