The Mann-Whitney U-test will be used to test the difference in rCBV between the two trial arms by tumor grade categorization (low and high grade) and between patients with high-grade and low-grade gliomas, within each of the two study arms at the significant level of 5%. The analysis will be performed for off-site assessment and presented for each off-site reader and overall (taking into account the consensus decision).

If more than one lesion were detected by a reader, the maximum value for rCBV will be considered for the analysis at reader level. For the overall rCBV analysis taking into account the consensus decision, the maximum value for rCBV of consensus reading will be considered. If no consensus was needed, the maximum value for rCBV between the two off-site readers will be considered.

Two analyses will be performed. The first one will consider the gliomas' grade categorization (high-grade versus low-grade) according to the stratification factor used at randomization, the second one will use the tumor grade categorization as per histopathological results (if any) collected during the study.

Categorization as per histopathological results will be the following:

- Grade 1 and Grade 2 = Low grade,
- Grade 3 and Grade 4 = High grade.

The Benjamini-Hochberg method will be used to account for multiple testing for the two analyses separately.

Grade per categorization (high-grade versus low-grade) according to the stratification factor used at randomization will be cross tabulated with the categorization of the grade as per off-site reader assessment, by treatment arm.

If more than one lesion were detected by a reader, the worst grade according to rCBV will be considered. Then, for the overall analysis of grade according to rCBV taking into account the consensus decision, the worst grade according to rCBV of consensus reading will be considered. If no consensus was needed, the worst grade according to rCBV between the two off-site readers will be considered. Moreover, for patients with histopathological results, categorization of the grade per histopathology will be cross tabulated with the categorization of the grade as per off-site reader assessment, by treatment arm.

Categorization as per off-site reader assessment will be the following (according to the Imaging Charter V1.0):

- $rCBV < 1.75$ = Low grade,
- $rCBV \geq 1.75$ = High grade.

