Assessment and evaluation of the T2* signal intensity time curve at lesion level (on-site and off-site assessment)

T2* signal intensity time curve will be visually assessed by on-site and off-site readers for the reliability of the curve in providing sufficient information for diagnosis purpose.

For on-site assessment, the number and percentage of lesions for whom the reliability of the curve provides suffice information will be tabulated by trial arms.

For the off-site assessment, the number and percentage of lesions for whom the reliability of the curve provides suffice information will be tabulated by trial arms.

CONFIDENTIAL	STATISTICAL ANALYSIS PLAN N° GDX-44-016 VERSION N° 4.0 (REF I011622)	F015830-03 Page 26 / 35
--------------	--	----------------------------

For lesions for whom the reliability of the curve provides suffice information, confidence in diagnosis will be presented, for each arm, by on-site readers and for the off-site assessment for each off-site reader, using a 5-point scale:

- 1 = nil: very uncertain,
- 2 = poor: uncertain,
- 3 = moderate: moderately certain,
- 4 = high: good certainty,
- 5 = excellent: very certain.

Confidence in diagnosis will be summarized qualitatively and quantitatively by trial arm. The on-site and off-site read outcomes will be separately analyzed.

For the overall reliability of the T2* signal intensity time curve taking into account the consensus decision, the worst confidence in diagnosis between the two readers will be considered if no consensus decision was needed (worst case scenario).

Assessment and evaluation of the T2* signal intensity time curve (off-site assessment)

Only for off-site readers, FWHM and the maximum signal drop will be tabulated at lesion level by off-site reader and compared between the trial arms using a Mann-Whitney U-test.

For the overall FWHM taking into account the consensus decision, the mean of values between the two readers for each lesion will be considered if no consensus decision was needed.

For the overall maximum signal drop taking into account the consensus decision, the maximum of values between the two readers for each lesion will be considered if no consensus decision was needed.

If the curve is not reliable, no calculation of FWHM and the maximum signal drop will be performed.

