Table 14.2.2.28 Reliability of the T2* signal intensity time curve for diagnosis and level of diagnosis confidence by treatment arm assigned at randomization and by grade (stratification variable at randomization) at Lesion Level – Off-site PPS

Table 14.2.2.29 Reliability of the T2* signal intensity time curve for diagnosis and level of diagnosis confidence by treatment arm assigned at randomization at Lesion Level – Off-site FAS

Table 14.2.2.30 Reliability of the T2* signal intensity time curve for diagnosis and level of diagnosis confidence by treatment arm assigned at randomization and by grade (stratification variable at randomization) at Lesion Level – Off-site FAS

Table 14.2.2.31 Reliability of the T2* signal intensity time curve for diagnosis and level of diagnosis confidence by treatment arm assigned at randomization at Lesion Level – On-site PPS

Table 14.2.2.32 Reliability of the T2* signal intensity time curve for diagnosis and level of diagnosis confidence assessed by treatment arm assigned at randomization and by grade (stratification variable at randomization) at Lesion Level – On-site PPS

Table 14.2.2.33 Reliability of the T2* signal intensity time curve for diagnosis and level of diagnosis confidence assessed by treatment arm assigned at randomization at Lesion Level – On-site FAS

Table 14.2.2.34 Reliability of the T2* signal intensity time curve for diagnosis and level of diagnosis confidence assessed by treatment arm assigned at randomization and by grade (stratification variable at randomization) at Lesion Level – On-site FAS

Table 14.2.2.35 Full-Width at Half-Maximum and Maximum signal drop by treatment arm assigned at randomization at Lesion Level – Off-site PPS

Table 14.2.2.36 Full-Width at Half-Maximum and Maximum signal drop by treatment arm assigned at randomization and by grade (stratification variable at randomization) at Lesion Level – Off-site PPS

Table 14.2.2.37 Full-Width at Half-Maximum and Maximum signal drop by treatment arm assigned at randomization at Lesion Level – Off-site FAS

Table 14.2.2.38 Full-Width at Half-Maximum and Maximum signal drop by treatment arm assigned at randomization and by grade (stratification variable at randomization) at Lesion Level – Off-site FAS

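### Off-site FWHM and maximum signal drop are tested between arms on lesions, so the 5% level is exceeded if some patients contribute several correlated lesions

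*SAP*

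**What the plan says.** SAP section 5.5.3 states that, for the off-site readers, FWHM and maximum signal drop "will be tabulated at lesion level by off-site reader and compared between the trial arms using a Mann-Whitney U-test". Section 2.2.2 confirms the unit: analyses of "FWHM and maximum signal drop will be performed at lesion or lesion / reader level". The overall two-reader values in section 5.5.3 (the readers' mean for FWHM, their maximum for signal drop, when no consensus was needed) are formed for each lesion, so they stay at lesion level. Tables 14.2.2.35 to 14.2.2.38 follow suit, for example "Full-Width at Half-Maximum and Maximum signal drop by treatment arm assigned at randomization at Lesion Level". Section 3.1 sets 5% two-sided for every test.

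The SAP expects that a patient may have more than one lesion off-site. Section 1.2 lists a differing lesion count between readers as a reason for consensus. The rCBV part of section 5.5.3 has a reduction rule: "If more than one lesion were detected by a reader, the maximum value for rCBV will be considered for the analysis at reader level". Section 2.2.2 equates the two levels only for the on-site read: "analyses for on-site reader at patient level are equivalent to lesion level as only one lesion is considered".

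A lesion enters the FWHM and signal-drop analysis only if its curve is usable: "If the curve is not reliable, no calculation of FWHM and the maximum signal drop will be performed".

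Protocol section 11.3.6.2 names the same test but no lesion unit, and it counts patients, not lesions, when tabulating curve reliability. SAP section 4, on changes to the planned analyses, describes only the dropped interim analysis.

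**The concern.** The arms were formed by randomising patients (SAP section 1.2). All lesions of a patient come from the same injection, scanner and acquisition. Preload use, injection rate above the 4 mL/s minimum, manufacturer and field strength may all differ between patients. Positive correlation between lesions of one patient is therefore plausible, although the documents do not quantify it.

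The ordinary Mann-Whitney variance treats every lesion as a separate independent observation. If lesions cluster in patients, that variance is too small, the p-value is too small, and multi-lesion patients carry extra weight. A difference in curve shape between two agents given at different doses could then be reported when there is none. I found no clustered rank test, mixed model or per-patient summary for these measures in either document. The Benjamini-Hochberg adjustment in SAP section 3.8 is for rCBV only and does not address clustering.

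**Working it through.** **Inputs from the documents.** 62 evaluable patients per arm (SAP section 3.3); Mann-Whitney test on lesions (5.5.3); 5% two-sided (3.1).

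**Inputs assumed.** The share of patients with several measured lesions, the number of lesions in those patients, and the within-patient correlation ρ. None is in the documents, so a range is shown.

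**The plan's own figure.** The only calculated sample size is for the primary endpoint: (1.960 + 0.842)² × 2 × 0.94 × 0.06 / 0.12² = 61.5, so 62 per arm. Power at 62 is 80.3%. For dropout, 124 / 0.9 = 137.8, so 138. These agree with the SAP. No sample size or power is stated for FWHM or signal drop; the 62 serves only as patients per arm.

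**Approximate level by formula.** With k lesions per patient:

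- design effect D = 1 + ρ × (E[k²]/E[k] − 1)
- true level ≈ 2 × (1 − Φ(1.96/√D))

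Example, 10% of patients with two lesions and ρ = 0.5: E[k] = 0.9 + 0.1 × 2 = 1.1; E[k²] = 0.9 + 0.1 × 4 = 1.3; D = 1 + 0.5 × (1.3/1.1 − 1) = 1.091; level ≈ 6.1%.

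**Simulated level.** 200,000 trials per setting with no arm difference, 62 patients per arm, a normal patient effect, and 3, 6 or 19 patients per arm (5%, 10%, 30%) with several lesions. Monte Carlo error is at most 0.1 point.

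| Assumed lesion pattern | Lesions in total | ρ = 0.3 | ρ = 0.5 | ρ = 0.8 | Formula, ρ = 0.3 to 0.8 |
|---|---|---|---|---|---|
| One lesion each | 124 | 5.0% | 5.0% | 5.0% | 5.0% |
| 5% with two | 130 | 5.3% | 5.5% | 5.7% | 5.3-5.9% |
| 10% with two | 136 | 5.5% | 6.0% | 6.6% | 5.6-6.7% |
| 30% with two | 162 | 6.6% | 7.6% | 9.3% | 6.6-9.4% |
| 10% with three | 148 | 6.6% | 7.7% | 9.5% | 6.8-9.8% |
| 30% with three | 200 | 8.8% | 11.7% | 15.7% | 9.0-15.5% |

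At ρ = 0 the simulated level is 4.9-5.1% in every pattern. The last row is an extreme case without support in the documents.

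**After reduction to one mean per patient.** The level is 4.8-5.1% in all settings.

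**Mean or maximum over lesions.** The number of lesions detected is itself read after injection, so it could differ by arm. With no true difference in values, 60,000 trials, and an assumed multi-lesion share of 10% in one arm and 30% in the other, at ρ = 0.3/0.5/0.8:

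- the maximum per patient rejects in 8.3/7.2/5.8% of trials with two lesions, and 11.9/10.0/6.7% with three
- the mean per patient rejects in 4.9-5.1%

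**The case against.** The strongest reply is that the problem may not arise. Eligibility concerns a primary glial tumour, the protocol writes of the tumour and the lesion in the singular, and the SAP treats several lesions as a contingency. The Imaging Charter, which the SAP cites and which is not available here, may limit how many lesions are measured. This stands: the fault is conditional, and with 5 to 10% of patients having two lesions the level moves only to 5.3-6.6%.

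Secondly, these are supplementary tests with no multiplicity control. Two independent 5% tests already give 1 − 0.95² = 9.75% for at least one false positive, and these are repeated by reader, overall, and on two analysis sets. That is true and limits the weight of the point. But it does not justify a single p-value that misses its stated level.

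Thirdly, the SAP chose the lesion as its unit, and a patient mean changes what is compared. That is fair. A rank test that accounts for lesions within patients would keep the lesion as the unit and would also be acceptable. It is an alternative remedy and not a defence of the unadjusted test.

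Finally, the SAP's rCBV rule uses the maximum over lesions, which the last calculation above advises against for FWHM and signal drop. The rCBV tests are free of the clustering problem because they use one value per patient; their sensitivity to lesion count is a separate matter.

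**Conclusion.** The concern holds as a conditional statement. As written, the off-site between-arm tests of FWHM and maximum signal drop do not hold 5% when some patients have two or more lesions with reliable curves and positively correlated values. The excess is below one percentage point if 5% of patients have two such lesions, up to 1.6 points if 10% do, and up to 4.3 points if 30% do, for correlations of 0.3 to 0.8. It is nil with one measured lesion per patient or with no correlation. The size in this trial cannot be fixed from the documents.

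No success criterion depends on these tests, and the primary non-inferiority analysis, which uses one value per patient, is untouched. The change should be made because the tests are meant to compare the agents and the remedy is cheap.

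**What to change.** In SAP section 5.5.3:

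1. Keep the existing rules for combining the two readers within a lesion, including the provision for consensus. Say which lesions and values count when consensus was needed or when the readers detect different numbers of lesions; this has to be clear whichever unit is used.
2. For each reader and overall, take the mean over a patient's lesions with a reliable curve as that patient's single value, and apply the Mann-Whitney test to those values. Do not use the maximum over lesions.
3. Keep the lesion-level results in Tables 14.2.2.35 to 14.2.2.38 as description only, and report the number of measured lesions per patient by arm.

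If the lesion must remain the unit, specify a rank test that accounts for clustering within patients.

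The cost is SAP wording and a small programming change. In the scenarios above, 124 patient values would enter the test instead of 130 to 200 lesion values. The mean also describes a patient's average curve and not the most abnormal lesion. If every patient has one measured lesion, the result is the same as under the present rule.

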5.6. Safety Evaluation

5.6.1. Extent of Exposure

The extent of exposure summary will be presented using the SS.

Duration (in days) between ICF signature and the IMPs administration, time from IMP administration to patient's last contact date, time from signature of ICF to patient's last contact date and time from MRI and histopathology will be tabulated by arm.

Descriptive statistics of the actual total volume (including the preload and main bolus) of IMPs will be presented by arm. Descriptive statistics of the actual volume of the preload bolus of IMPs will be presented by arm.

Occurrence of overdose (if any), actual injection rate of administration, brand of power injector used and volume of saline flush injected (if any) will be tabulated by arm.

Frequency tabulation of actual injection rate will be also displayed per arm according to following classes:

- ≥ 4 mL/s and ≤ 6 mL/s,
- > 6 mL/s.

Listing of extent of exposure and exposure will be presented in CSR appendix 16.2.1 and 16.2.7, respectively.

5.6.2. Adverse Events

NTEAEs

An overall summary of NTEAEs will be presented using the SPS. The table will be presented with the overall "Total" column only.

CONFIDENTIAL	STATISTICAL ANALYSIS PLAN N° GDX-44-016 VERSION N° 4.0 (REF I011622)	F015830-03 Page 27 / 35
--------------	--	----------------------------

The total number of events and number of patients with at least one event will be tabulated for the following events:

- All NTEAEs,
- NTEAEs according to intensity (patients with AEs having different intensities will be counted in each category of intensity),
- NTEAEs according to the outcome (patients with AEs having different outcomes will be counted in each category of outcome),
- NTEAEs requiring an AE-targeted medication,
- NTEAEs requiring another AE-targeted action,
- NTEAEs leading to study discontinuation,
- Serious NTEAEs (variable “serious” classified as yes or missing) and by seriousness criteria (patients with AEs having different seriousness criteria will be counted in each category of seriousness criterion),
- AEs of special interest (AESIs) (preferred term is Nephrogenic systemic fibrosis).
- AEs with causal relationship to a study procedure.

Furthermore, the distribution of the number of AEs reported by patient (0, 1, 2 or 3 or more AEs) will be also presented.

The number and percentage of patients with at least one NTEAE and the number of NTEAE will be presented overall according to Primary SOC and PT.

TEAEs

The same overview will be displayed by arm for Treatment Emergent AEs (TEAEs) using the SS. The terms “NTEAE” will be replaced by “TEAE”. The following variables will be presented in addition:

- TEAEs with causal relationship to the IMP.
- TEAEs leading to interruption of the IMP.

The number and percentage of patients with at least one TEAE and the number of TEAE will be presented by arm and overall according to Primary SOC and PT.

TEAEs with Causal Relationship to the IMP

The number and percentage of patients with at least one TEAE with causal relationship to the IMP and the number of corresponding TEAE will be presented by arm and overall according to Primary SOC and PT. AEs with causal relationship to the IMP are those described by the investigator with causal relationship to the IMP “related” or missing.

TEAEs with Causal Relationship to a Study Procedure

The number and percentage of patients with at least one TEAE with causal relationship to a study procedure and the number of corresponding TEAE will be presented by arm and overall according to Primary SOC and PT. AEs with causal relationship to a study procedure are those described by the investigator with causal relationship to a study procedure “related”.

TEAEs requiring an AE-targeted medication

The number and percentage of patients with at least one TEAE (whatever the causal relationship) requiring an AE-targeted medication and the number of corresponding TEAE will be presented by arm and overall according to Primary SOC and PT.

TEAEs requiring an AE-targeted therapeutic measure

The number and percentage of patients with at least one TEAE (whatever the causal relationship) requiring another AE-targeted action and the number of corresponding TEAE will be presented by arm and overall according to Primary SOC and PT.

CONFIDENTIAL	STATISTICAL ANALYSIS PLAN N° GDX-44-016 VERSION N° 4.0 (REF I011622)	F015830-03 Page 28 / 35
--------------	--	----------------------------

TEAEs requiring an AE-targeted procedure

The number and percentage of patients with at least one TEAE (whatever the causal relationship) requiring another AE-targeted action and the number of corresponding TEAE will be presented by arm and overall according to Primary SOC and PT.

TEAEs requiring trial discontinuation

The number and percentage of patients with at least one TEAE (whatever the causal relationship) requiring trial discontinuation and the number of corresponding TEAE will be presented by arm and overall according to Primary SOC and PT.

TEAEs requiring IMPs interruption

The number and percentage of patients with at least one TEAE (whatever the causal relationship) requiring IMPs interruption and the number of corresponding TEAE will be presented by arm and overall according to Primary SOC and PT.

Serious TEAEs

The number and percentage of patients with at least one serious TEAE (whatever the causal relationship, related to IMPs and related to the study procedure itself) and the number of corresponding serious TEAE will be presented by arm and overall according to Primary SOC and PT.

Serious TEAEs with Causal Relationship to the IMP

The number and percentage of patients with at least one serious TEAE with causal relationship to the IMP and the number of corresponding serious TEAE will be presented by arm and overall according to Primary SOC and PT.

Serious TEAEs with Causal Relationship to a Study Procedure

The number and percentage of patients with at least one serious TEAE with causal relationship to a study procedure and the number of corresponding serious TEAE will be presented by arm and overall according to Primary SOC and PT.

Serious TEAEs leading to death

The number and percentage of patients with at least one serious TEAE (whatever the causal relationship) leading to death and the number of corresponding serious TEAE will be presented by arm and overall according to Primary SOC and PT.

AESI

The number and percentage of patients with at least one AESI (whatever the causal relationship) and the number of corresponding AESI will be presented by arm and overall according to Primary SOC and PT.

All tables will be sorted by descending frequency of SOC and, within each SOC by descending frequency of PT according to the overall column.

Deaths, serious adverse events and other significant adverse events

Deaths, SAEs and AESI will be listed (if any). These listings will be sorted by patient number, actual treatment arm, date/time of IMPs administration, date/time of onset of the AE, end date, Primary SOC, PT, and description.

Listing of adverse events will be presented in CSR appendix 16.2.7.

